#### 5.1.2. Digit Symbol Substitution Test Repeatable Battery for the Assessment of Neuropsychological Status Version

The DSST RBANS will serve as the primary efficacy endpoint. To complete the DSST RBANS form, participants will receive a symbol and must match the number, as quickly and accurately as possible, within 90 seconds. The number of correct symbol/number pairings determines the participants score.

### 5.2. British Columbia Cognitive Complaints Inventory

The BC CCI was developed to measure cognitive complaints in individuals with MDD (Iverson and Lam 2013). It is a 6-item self report measure that asks respondents to rate problems with specific cognitive symptoms over the past 7 days. A 4-point scale (0 “Not at all” to 3 “Very much”) is used to rate each item. The total score (ranges from 0 to 18) that is generated assesses domains of memory, concentration, trouble expressing thoughts, word finding, and problem solving. Higher scores indicate greater severity of cognitive impairment.

Four categories of cognitive complaints have been defined for the BC-CCI total score:

- Broadly normal: 0 to 4
- Mild: 5 to 8
- Moderate: 9 to 14
- Severe: 15 to 18

Three additional, non-scored, items that ask about how these symptoms impact work, relationships and social/recreational activities are also included to provide further information on the nature of functional impairment.

### **5.3. Patient Global Impression of Severity**

The PGI-S is a 5-point Likert type rating scale and a widely used assessment in clinical psychopharmacology trials to assess severity of illness ([FDA 2018](#)). Participants will be asked to rate the level of severity of their problems with concentration, memory, and thinking skills during the past 7 days. The responses options are as follows:

- None (0)
- Mild (1)
- Moderate (2)
- Severe (3)
- Very severe (4)

### **5.4. Epworth Sleepiness Scale**

The ESS is a self-administered questionnaire with 8 questions ([Johns 1991](#)). Respondents rate on a 4-point scale (0 to 3) their usual chances of dozing off or falling asleep while engaged in 8 different activities. Most people engage in those activities at least occasionally, although not necessarily every day. The ESS total score (the sum of 8 item scores, 0 to 24) can range from 0 to 24. Higher ESS total scores are associated with higher sleep propensity in daily life, also referred to as 'daytime sleepiness'.

## 6. ANALYSIS POPULATIONS

### 6.1. Enrolled Population

The Enrolled Population will include all subjects who sign the informed consent form. This population will be used for analyses of all enrolled subjects disposition.

### 6.2. Safety Population

The Safety Population will consist of all randomized participants who received at least 1 dose of study intervention. This analysis set will be used for safety analyses and participants should be summarized according to actual treatment. This population will be analyzed for safety evaluations and will be presented in the tables and listings of safety data.

### 6.3. Intent-To-Treat (ITT) Population

The Intent-to-Treat (ITT) Population will consist of all randomized participants. [REDACTED]

### 6.4. Modified Intent-To-Treat (mITT) Population

The modified Intent-to-Treat (mITT) population will consist of all participants who were randomized, received at least 1 dose of study medication, and have Baseline and at least 1 postdose evaluation of the DSST RBANS. If a participant in the mITT population does not have an assessment for a particular endpoint, the missing assessment will be excluded in the analysis of that endpoint.

The primary efficacy analyses will be based on the mITT population.

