9.2. Sample Size Determination

A sample size of 49 participants per treatment sequence for a total sample size of 98 will provide 90% power to detect a difference of 3 points in means for the change from Baseline to Week 2 on DSST RBANS scores between solriamfetol and placebo, assuming a standard deviation of 9 points in the change in DSST (the cross over analysis of variance [ANOVA] root mean squared error (RMSE) is 6.36). The sample size estimates are based on the results from Trintellix randomized parallel placebo-controlled trials ([McIntyre 2014](#); [Mahableshwarkar 2015](#)). The change from Baseline to Week 8 resulted in an estimated delta on DSST performance score of 1.8 ~ 4.3 (average 3.4) and SD of 6.6 ~ 8.6. Another reference is a crossover study with 5 dosages of MK-0249, modafinil 200 mg, and placebo and each period is 2 weeks, the RMSEs are estimated from 4.4 ~ 5.7 ([Herring 2013](#)). It is increased to 6.36 to account for uncertainty in sample size assumptions. A 1-sided significance level of 0.025 using a 2 group t-test (crossover ANOVA) is used in the sample size calculation. Assuming a correlation of 0.5 between periods on DSST, a delta of 3, a standard deviation of 9, and a 15% dropout rate, a total of 116 (58 participants per treatment sequence) will be randomized.

Note: “Randomized” means a participant who consented to the study and was assigned to a randomized treatment group and received at least 1 dose of study intervention.

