9.3. Analysis Populations

Population	Description
Safety	All randomized participants who receive at least 1 dose of study intervention. This analysis set will be used for safety analyses and participants should be summarized according to actual treatment. This population will be analyzed for safety evaluations and will be presented in the tables and listings of safety data.
ITT	All randomized participants.
mITT	All participants who were randomized, received at least 1 dose of study medication, have Baseline and at least 1 postdose evaluation of DSST. If a participant in the mITT population does not have an assessment for a particular endpoint, it will be excluded in the analysis of that endpoint. The primary efficacy analyses will be based on the mITT population.

Abbreviations: DSST = Digit Symbol Substitution Test; ITT = Intent-to-Treat; mITT = modified ITT

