9.4.1.3. Intercurrent Event Strategies

The following are intercurrent events that may occur during the study:

- Study treatment discontinuation due to AEs, lack of efficacy or use of other (prohibited) concomitant medications, etc.
- Withdrawal from the study

- Lost to follow-up

Participant's DSST data will not be collected if the participant discontinues the treatment (while on treatment policy strategy). Missing assessments after discontinuation of treatment due to AE, lack of efficacy, or any other reasons will not be imputed for primary analysis.

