9.4.6. Other Analyses

There are no other analysis (eg, subgroups of interest) planned for this study.

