#### 10.1.1. Derivations of the Primary Efficacy Variable

The primary efficacy variable is the change from baseline in the average of the DSST RBANS scores at the end of each double-blind treatment period. The change will be calculated as:

$$\text{Change} = \text{Post Baseline} - \text{Baseline}$$

A positive change is indicative of improvement.

The estimand will be based on the following four attributes:

1. Population: defined through study design and inclusion/exclusion criteria outlined in Sections 5.1 and 5.2 of the protocol to reflect the targeted patients with EDS associated with OSA plus impaired cognitive functioning;
2. Variable: change from baseline to end of active treatment in the average of the DSST RBANS scores;
3. Intercurrent event: no intercurrent events to be taken into account;
4. Population-level summary: the difference in the primary variable means between active and placebo conditions.

The estimand is then the difference in means between active and placebo in the change from baseline in the primary measurement in the targeted participant population.

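### The primary DSST result is an effect in participants who supply both treatment periods, but SAP 10.1.1 states it for the whole targeted population

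*SAP*

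**What the plan says.** Protocol 9.3 states that "The primary efficacy analyses will be based on the mITT population". SAP 6.4 defines that set as randomised participants who "received at least 1 dose of study medication, and have Baseline and at least 1 postdose evaluation of the DSST RBANS".

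The schedules (Protocol Table 3, SAP Table 2) place the DSST RBANS at Visits 1, 3, 5 and 8, and not at the safety follow-up or early discontinuation visit. Dosing starts the day after Visit 3 (Protocol 4.1.3), so Visit 5, the last day of Period 1, gives the first postdose score. A participant who stops permanently goes to the follow-up or early discontinuation visit (Protocol 7.1), and interruption is not allowed (Protocol 7.1.1).

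Protocol 9.4.1.3 says DSST data are not collected after stopping and adds: "Missing assessments after discontinuation of treatment due to AE, lack of efficacy, or any other reasons will not be imputed for primary analysis". SAP 10.4 repeats the no-imputation rule in general terms.

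The primary model in Protocol 9.4.2 and SAP 10.1.2 lists sequence, participant within sequence, treatment and period as fixed effects, with the baseline average as covariate.

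On what is being estimated, SAP 4.1 restricts the population to mITT and describes a while-on-treatment handling of stops. SAP 10.1.1 says no intercurrent events are taken into account and gives the estimand for a group that it defines by the eligibility criteria: "The estimand is then the difference in means between active and placebo in the change from baseline in the primary measurement in the targeted participant" (the quoted sentence is cut before its last word).

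**The concern.** The plan itself names adverse events and lack of efficacy as reasons for stopping, and both can depend on treatment. Participants who stop for these reasons are absent from the primary contrast, yet the result would be read as the effect in adults with sleepiness due to OSA and impaired cognition. If solriamfetol stoppers gain less than those who stay on it, the reported difference is too large for that population. No analysis in the readable text would show by how much: the Per Protocol set is a subset of mITT (SAP 6.5), and Protocol 9.4.6 says "There are no other analysis (eg, subgroups of interest) planned for this study". By contrast, SAP 10.2 counts missing values as failures in the secondary responder analyses, so the primary endpoint is handled less cautiously than those.

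**Working it through.** **Inputs** (Protocol 9.2, repeated in SAP 10.7): difference 3 points, SD of change 9, between-period correlation 0.5, crossover RMSE 6.36, 1-sided 0.025, dropout 15%, 116 randomised (58 per sequence). The 15% is not split by treatment, period or reason.

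**Plan's own figure.**
- SD of the within-participant difference = 9 x sqrt(2 x (1 - 0.5)) = 9.0; RMSE = 9/sqrt(2) = 6.364.
- SE of the treatment difference at 49 per sequence = 6.36/sqrt(49) = 0.909.
- Noncentral t with 2n - 2 df: power is 89.9% at 48 per sequence and 90.5% at 49.
- 98/0.85 = 115.3, which rounds up to 116.

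The stated sample size reproduces.

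**Who reaches the contrast.**
- Stop in Period 1: no Visit 5 score, none later, so outside mITT.
- Stop in Period 2: in mITT with one score. With a separate fixed parameter for each participant, a single score is fitted exactly and carries no information on treatment.

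A check fit on one simulated crossover of 116, with 17 participants lacking Period 2, gave an estimate of 3.774, SE 0.872 and 97 residual df, whether those 17 were included or removed.

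Both kinds of stop are lost, on either treatment. The mITT rule is only part of the cause; missing data without imputation plus the fixed participant term does the rest.

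**Size.** Let f be the share of all dropouts, in either period, who stop solriamfetol and have effect e. Assume everyone else has the planned 3 points.
- Effect in all dosed participants = 3 x (1 - 0.15f) + e x 0.15f
- Overstatement = 0.15f x (3 - e), which is 3 x 0.15f when e = 0

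| f | Expected stoppers (of 17.4) | Effect in all, e = 0 | Overstatement, e = 0 | As % of 3 | In SEs of 0.909 | Overstatement, e = 1.5 | Overstatement, e = -3 |
|---|---|---|---|---|---|---|---|
| 0.25 | 4.35 | 2.89 | 0.11 | 3.75% | 0.12 | 0.06 | 0.23 |
| 0.5 | 8.7 | 2.78 | 0.23 | 7.5% | 0.25 | 0.11 | 0.45 |
| 1 | 17.4 | 2.55 | 0.45 | 15% | 0.50 | 0.23 | 0.90 |

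The values of f and e are assumptions; the documents give neither. For orientation, dropout falling equally on the two treatments, with zero effect in every solriamfetol stopper, is f = 0.5.

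**The case against.** The strongest reply is that restricting to mITT without imputation is the estimand that SAP 4.1 declares, so leaving stoppers out is a design choice and not a bias. Moreover, a removed participant leaves both conditions, so the remaining comparison is still within-participant. Both statements are right. They protect the internal comparison, but not the step to the targeted population in SAP 10.1.1, which is where the two SAP sections conflict.

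Four stronger readings are tempting, and the documents do not support them.

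- *The mITT rule alone could inflate the effect by up to 15%.* Through stops before Visit 5, that would need all 17.4 expected dropouts to be solriamfetol stops in the sequence that takes it first: 17.4/58 = 30% of that sequence and none elsewhere. If dropout were even over sequences and periods, that cell would account for 3.75%. Nor is 15% a ceiling, as the e = -3 column shows.
- *The bias certainly favours solriamfetol.* Placebo stops are lost too, and nothing in the documents says that stoppers gain less on the DSST. The direction is conditional.
- *The selection is lopsided because a solriamfetol stopper in Period 2 stays in mITT with a placebo score.* Under the fixed participant term that score does not affect the contrast. If participant were in practice fitted as random, Period 2 stoppers could contribute something, but Period 1 stoppers still could not.
- *No sensitivity analysis exists.* Text after the ITT definition in SAP 6.3 is redacted, SAP 10.6 is not visible, and the no-imputation statement in Protocol 9.4.1.3 is limited to the primary analysis. Absence cannot be asserted.

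It is also fair that the size calculation follows directly from its assumptions and is not evidence of bias in this trial, and that disposition with reasons will be reported by sequence (SAP 8.1), so the number lost will be visible.

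**Conclusion.** The point holds as a mismatch between what the primary analysis can estimate and the population for which SAP 10.1.1 states it. The mechanism follows from the schedule, the missing-data rule and the model, and needs no assumption beyond participant being fitted as a fixed effect, as written.

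The size is conditional. With zero effect in solriamfetol stoppers it runs from about 0.11 to 0.45 points on a planned 3, or 0.12 to 0.50 standard errors over f = 0.25 to 1; it is smaller if stoppers keep part of the benefit and larger if they do worse on drug than on placebo. The planning figures may not describe the final data: SAP 10.7 says the new sponsor has decided to conclude the study and presents 116 and 15% as the pre-amendment justification. This does not invalidate the primary analysis, but it limits what may be concluded from it.

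**What to change.** Keep the mITT analysis as primary. Before database lock:

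1. In SAP 10.1.2 and 10.4, prespecify one sensitivity analysis in all randomised and dosed participants with a Baseline DSST RBANS. Solriamfetol values missing after a stop for adverse event or lack of efficacy are multiply imputed from the placebo distribution for that period given baseline; all other missing values are imputed under missing at random. Report the difference and 95% CI beside the primary result.
2. Word the primary result as the effect in participants who completed both treatment periods.
3. Reconcile SAP 4.1 and 10.1.1 on population and intercurrent events.
4. If a redacted section already holds a sensitivity analysis, check that it covers all dosed participants with imputation. An ITT analysis without imputation would return the same answer as the primary one.

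The cost is SAP text and some programming, with no new visits, data or participants; reasons for discontinuation are already summarised. The sensitivity estimate will usually be somewhat smaller. By construction it assumes no drug benefit in the imputed solriamfetol values, so it shows how far the conclusion depends on the missing participants, not what their true effect was.

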### 6.5. Per Protocol Population

The Per Protocol population will include all mITT participants without important major protocol violations. The criteria for important major protocol violation will be determined and documented prior to database lock and unblinding of treatment codes. Participants with important major protocol violations will be flagged in data listings.

Additional efficacy analyses may be performed on the Per Protocol population.

## 7. GENERAL CONVENTIONS

Unless otherwise stated, all analyses will be performed using SAS Version 9 and all hypothesis tests will be conducted at a two-sided significance level of 0.05. P-values will be presented with 3 decimals and p-values that are less than 0.001 will be presented as <0.001.

Continuous data will be summarized using descriptive statistics: number of observations (n), mean, standard deviation (SD), median, minimum, and maximum. Frequencies and percentages will be used to summarize categorical (discrete) data. Presentations of categorical data will generally suppress percentages for items where the count is zero in order to draw attention to the nonzero counts. In general, mean, SD, median, minimum, maximum, and percentages will be presented with one decimal.

Unless otherwise stated, confidence intervals, when presented, will be constructed at the two-sided 95% level. For binomial variables, the 95% confidence intervals will be constructed using the normal approximation without continuity correction.

Data listings will present all data collected on case report forms (CRFs) by study drug, center, and participant number.

### 7.1. Definition of Baseline

Unless otherwise stated, the last observed measurement prior to or on the date of randomization will be considered the baseline measurement. For the primary endpoint, baseline for the DSST RBANS will be the average of the 4 DSST RBANS scores (2-, 4-, 6-, and 8 hour) at Visit 3.

### 7.3. SAP Version Control Convention

The first approved versions of the SAP will be numbered sequentially as Version 1.00. As mentioned in the introduction, the SAP may evolve over time due to reasons such as protocol amendment or regulatory feedback, the subsequent approved version(s) will be numbered as sequentially as Version 1.0i. The reason for the changes must be documented in the SAP history log. The final version to be used for the analysis must be filed before the database lock and labelled as Final Version 1.xy. The Clinical Study Report will document any changes made after the Final Version.

## **8. DESCRIPTION OF THE STUDY POPULATIONS**

All tables, figures, and listings must include a population descriptor (e.g., mITT, Safety, or Per Protocol) in the titles.

### **8.1. Disposition**

Participant disposition summaries will be presented by Sequence and will include the number of participants screened, randomized, and percentage of participants who complete the study. The summaries will also include the reasons for early discontinuation from the study.

Disposition summaries will be presented for Enrolled, Safety, mITT, ITT and Per Protocol (if applicable) populations separately.

### **8.2. Demographics and Baseline Characteristics**

A summary of demographics and baseline characteristics will be presented by the Sequence and overall, for the Safety, mITT, and Per Protocol (if applicable) populations. The demographic characteristics will, at the minimum, consist of age, sex, ethnicity, and race using descriptive statistics. Baseline characteristics may include the WAIS DSST score at screening (i.e., total number correct and age-scaled score).

### **8.3. Medical History**

A medical history listing will be presented for the Safety Population and may also be summarized.

## **9. PRIOR AND CONCOMITANT MEDICATIONS**

All medications recorded on the CRFs will be coded using the WHO Drug Dictionary Version B3 March 2021. Prior and concomitant medications will be summarized by treatment arm in the safety population by WHO Drug base substance preferred name.

Prior medications are defined as medications with stop dates occurring before the date of first administration of any study treatment. Concomitant medications are defined as medications with start dates occurring on or after the date of first administration of any study treatment and no more than 30 days after the last study visit. Medications with start and stop dates that bracket the date of first administration of a study treatment will be summarized as both prior and concomitant medications.

Medications that were clearly stopped prior to the date of first administration of a study treatment will be included in the prior medications table, and medications that were clearly started on or after the date of first administration of any study treatment component will be included in the concomitant medications table. All other medications will be included in both the prior and concomitant medications tables.

Prior and concomitant medications will be summarized for the Safety Population.

## 10. EFFICACY ANALYSES

### 10.1. Primary Efficacy Variable

The primary objective of the study is to evaluate the efficacy of solriamfetol as measured by the change from baseline (Visit 3) in the average of the DSST RBANS scores at the end of each double-blind treatment period, where the average is the average of non-missing scores from Hours 2, 4, 6, and 8. It should be noted that the scores obtained at the pre-dosing (practice) are performed to re-orient the participants for the test and these scores will not be included in the average.

#### 10.1.1. Derivations of the Primary Efficacy Variable

The primary efficacy variable is the change from baseline in the average of the DSST RBANS scores at the end of each double-blind treatment period. The change will be calculated as:

$$\text{Change} = \text{Post Baseline} - \text{Baseline}$$

A positive change is indicative of improvement.

The estimand will be based on the following four attributes:

1. Population: defined through study design and inclusion/exclusion criteria outlined in Sections 5.1 and 5.2 of the protocol to reflect the targeted patients with EDS associated with OSA plus impaired cognitive functioning;
2. Variable: change from baseline to end of active treatment in the average of the DSST RBANS scores;
3. Intercurrent event: no intercurrent events to be taken into account;
4. Population-level summary: the difference in the primary variable means between active and placebo conditions.

The estimand is then the difference in means between active and placebo in the change from baseline in the primary measurement in the targeted participant population.

#### 10.1.2. Primary Analyses

The primary efficacy variable, change from baseline in the average of the DSST RBANS scores, will be analyzed using a Mixed Model with Repeated Measures (MMRM). The model will include sequence, participant within sequence, treatment (solriamfetol and placebo), period as fixed effects, and the baseline average of the DSST RBANS scores as the covariate. The unstructured covariance for the repeated measurements will be assumed. The treatment effects, the 2 sided 95% confidence interval (CI) of treatment difference (solriamfetol – placebo) will be presented.

